A Disposable Device NAS to Treat Obstructive Sleep Apnea and Snoring

NCT02928770

December 5, 2014

[name], PhD, Principal Investigator Stanford University Stanford, California 94305

Statistical Analysis Plan

The primary endpoint that will be evaluated in the study would be the AHI efficacy of the NAS device by PSG comparisons. The PSG factors concerned will be compared between the two PSG evaluations conducted, the initial control PSG evaluation without the NAS device applied and the PSG evaluation with the NAS device applied.

As for the questionnaires, each questionnaire such as the ESS, the BQ, the MQ, the SSS, the SAQLI and etc., obtained will be analyzed for determining qualitative factors regarding quality of life and sleep qualities. In addition, these questionnaires and interviews will be valuable resources regarding safety issues as well.

The secondary endpoint that will be evaluated in the study would be the safety of the NAS device. Interviews and questionnaires would be the mode of evaluation regarding the safety factors. The ultimate goal of safety would be finishing this clinical study without any adverse events or accidents that harm the subjects physically.

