2. STUDY PROCEDURES

a. Procedures

This research study is seeking to enroll up to 30 participants with OSA and snoring. The enrollment will be at Stanford Sleep Medicine Center. The NAS (straight type) supports the soft palate from "collapsing" by supporting it physically, as well as securing the passage of airflow both inside and outside of the tube. Participants in the proposed study will undergo any or all of the following procedures.

After the consent process (30 min), each participant will be asked to complete either paper questionnaires which inquires about his or her demographic information and medical history (Sleep Disorders Questionnaire, 30 min) and level of daytime sleepiness in various situations (Epworth Sleepiness Scale, 5 min) or an electronic questionnaire (Alliance Sleep Questionnaire, 20 min).

Each participant will be asked to submit to an initial evaluation (60 min), which consists of a discussion of the participant's sleep habits and problems, medical history of participant and family, review of systems, medications, education, employment, and personal habits. A general physical examination, including but not limited to examination of the mouth and throat, and measurements of his or her weight and height; circumference of neck, waist, and hip; pulse and respiration rate; and blood pressure.

The participants will undergo two sleep studies: one sleep study at our center prior to using the NAS device (Baseline) and another after 7 days of use of the device at their

homes (Treatment). The participants will wear the NAS device during the second sleep study.

The sleep study will be conducted in routine fashion, with recording electrodes and equipment attached to the participant to enable monitoring of the electroencephalogram (EEG, C3-A2 and C4- A1, O2-A1 and O1-A2), electro-oculogram (EOG, ROC-A1, LOC-A2), chin and anterior tibialis electromyograms (EMG), heart rate by two-lead electrocardiogram (EKG), snoring intensity (anterior neck microphone), nasal pressure (nasal cannula), oral airflow(thermocouple), thoracic and abdominal movement (inductance plethysmography bands), and oxygen saturation (pulse oximetry). The duration of the application of all of these electrodes and recording devices to the participant is approximately 1.5 hours. The polysomnogram will be scheduled to allow at least 7 hours but no more than 9 hours of time in bed for the participant during the night.

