In addition, recruitment flyers will be posted in local businesses, as well as running a subject recruitment newspaper ad to obtain subjects outside of the Stanford Sleep Medicine Center clinic population. The phone number and email address of the research coordinator will be on the ads for the interested participant to contact.

h. Eligibility Criteria

i. Inclusion Criteria

The population under study will be clinical outpatients 18 years of age or older with symptoms of obstructive sleep apnea and snoring, and with body mass index less than 30 kg/m2.

ii. Exclusion Criteria

Children, pregnant women, homeless, economically disadvantaged individuals, and those who are unable to comprehend or understand English, or follow instructions will be excluded. Persons with body mass index greater than 30 kg/m2 will also be excluded.

i. Screening Procedures

Patients at age over 18 will be screened. Clinical outpatients will be recruited from our normal clinic population. No telephone screening will be performed. In addition, flyers will be posted to recruit subjects outside of our normal clinic population.

j. Participation in Multiple Protocols

Our research team will ask this question, and this question will be on our informed consent form. Patients will be given the choice as to whether they want to participate in this study if they are already enrolled in another study.

k. Payments to Participants

The patient will be paid to participate in this research study. It is a cooperation fee of \$700. The payments will be prorated based on the length of participation. Payments may only be made to U.S. citizens, legal resident aliens, and those who have a work eligible visa. Patients may need to provide their social security number to receive payment.

Participants will have the option to receive the nasal device after the second sleep study. The participant will be allowed to receive complimentary nasal stents until the time the device becomes commercially available.

I. Costs to Participants

There is no cost for participating in this study, other than basic expenses like transportation and the personal time it will take to come to all of the study visits. The study will pay for those services, supplies, procedures, and care associated with the study that are not a part of routine medical care. The patient will be responsible for any copayments and/or deductibles as required by your insurance.

m. Planned Duration of the Study

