The Protocol Director will be monitoring all safety data from Stanford participants, and will determine if it remains safe for a subject to continue. A subject would be discontinued from the protocol at any time if it is determined that subject safety is at risk. The protocol director and/or study coordinator will be reachable by cell phone 24/7 by subjects.

Regarding an adverse/unexpected event, the lab personnel typically become aware of the event directly from the participant or the participant's healthcare provider. Upon becoming aware of an adverse event, the principal investigator should assess whether the adverse event represents an unanticipated problem:

1. unexpected;

2. related or possibly related to participation in the research; and

3. serious or otherwise one that suggests that the research places subjects or others at a greater risk of physical or psychological harm than was previously known or recognized.

e. Data Safety Monitoring Plan (DSMC)

i. Data and/or events subject to review

Data Collected From the Participant. Data from forms, questionnaires, and interviews will be entered into a secure, password-protected web portal. All data will also be collected and transferred in compliance with the Health Insurance Portability and Accountability Act (HIPAA).

ii. Person(s) responsible for Data and Safety Monitoring

The protocol director

iii. Frequency of DSMB meetings

Not Applicable

iv. Specific triggers or stopping rules

Within 24 hours of learning of a death, or within 5 days of learning of an unanticipated problem involving risks to participants or others.

v. DSMB Reporting

Not Applicable

vi. Will the Protocol Director be the only monitoring entity? (Y/N)

Not Applicable

vii. Will a board, committee, or safety monitor be responsible for study monitoring? (Y/N)

Not Applicable

f. Risks to Special Populations

Not Applicable

10. Benefits

Study participants will not receive direct benefit; however future sleep medicine patients may benefit. This information about NAS (nasal stent) appears to be a useful alternative or additive treatment for patients with OSA. We hope to gain through this study if this new device provides a better or alternative treatment of OSA.

11. **PRIVACY AND CONFIDENTIALITY**

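### Safety is assessed by interview and questionnaire, so worse breathing, saturation or EKG on the device-night sleep study is not counted as a safety outcome, although it is recorded

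*SAP*

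**What the plan says.** **Safety endpoint.** The SAP states: "The secondary endpoint that will be evaluated in the study would be the safety of the NAS device". The method follows: "Interviews and questionnaires would be the mode of evaluation regarding the safety factors". The stated aim is: "The ultimate goal of safety would be finishing this clinical study without any adverse events or accidents that harm the subjects physically". No safety variable, threshold or analysis is defined.

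**Role of the PSG.** The SAP gives it to efficacy: "The primary endpoint that will be evaluated in the study would be the AHI efficacy of the NAS device by PSG comparisons". It adds that PSG factors, which it does not name, will be compared between the night without the device and the night with it.

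**What is recorded.** Protocol section 2.a lists nasal pressure, oral airflow, respiratory effort, pulse oximetry and a two-lead EKG for the sleep study. There are two such studies, and the device is worn at the second.

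**Safety monitoring.** Section 9.d says the protocol director monitors all safety data and "will determine if it remains safe for a subject to continue". Staff are expected to learn of events from the participant or the participant's healthcare provider. Section 9.e.i, headed as the data and events subject to review, reads: "Data from forms, questionnaires, and interviews will be entered into a secure, password-protected web portal". It does not mention PSG results. Section 9.e.iv gives reporting timelines only.

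**After the second PSG.** Section 8.k says: "Participants will have the option to receive the nasal device after the second sleep study". Sections 2.a and 8.e make the same offer. Sections 2.a and 8.k run it until the device is on the market, and section 2.a asks for the Epworth scale every three months meanwhile. Section 2.a also schedules a close-out visit at which the study doctor goes over both PSGs with the participant.

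**The concern.** The device is a tube passed through one nostril and worn during sleep by people with symptoms of OSA. If it made breathing worse in some of them, the evidence would be more respiratory events, lower saturation or a changed EKG on the device night. The wearer is asleep, so an interview is a poor instrument for this. The questionnaires that the SAP names are to be analysed for quality of life and sleep quality, and their safety use is not specified.

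The study therefore records the relevant data twice per participant but gives them no stated place in the safety endpoint. A report that follows the SAP could show a favourable mean AHI change and no safety events, and leave the reader unable to see how many participants had a worse night with the device. The continued supply of stents makes this more than a reporting matter, because the documents do not say how the device-night result bears on that supply.

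**Working it through.** The plan gives no figure to reproduce: it states 30 participants with no AHI mean, SD, effect size, alpha or power. The main check is therefore textual; the arithmetic only illustrates.

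**Step 1. Where each signal is counted.**

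| Signal on the device night | Recorded (Protocol 2.a) | Efficacy (SAP) | Safety (SAP) |
|---|---|---|---|
| AHI | yes | yes, primary comparison | not named |
| Oxygen saturation | yes | possibly, among the unnamed PSG factors | not named |
| EKG | yes | possibly, among the unnamed PSG factors | not named |
| Participant's report | yes | quality of life and sleep | yes, the stated mode |

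No PSG variable is assigned to safety in either document.

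**Step 2. Can a good mean coexist with individual worsening?** Assume that individual AHI changes are normal, and let dz = mean fall / SD of change. Then the share with a higher AHI on the device night is 1 - Phi(dz). If a paired t-test were used with n = 30 (the SAP names no test), a result just reaching two-sided p = 0.05 has dz = 2.045 / sqrt(30) = 0.37.

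| dz (assumed) | Share with higher AHI | Expected of 30 |
|---|---|---|
| 0 (no effect) | 50% | 15 |
| 0.37 | 35% | 10.6 |
| 0.5 | 31% | 9.3 |
| 0.8 | 21% | 6.4 |
| 1.0 | 16% | 4.8 |

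In AHI units, an assumed SD of 15 events/h and a mean fall of 5 give dz = 5/15 = 0.33 and a share of 37% (about 11 of 30). A mean fall of 10 gives dz = 0.67 and 25% (about 8 of 30). The SD has no source in the documents; a smaller SD lowers these shares and a larger one raises them towards 50%. All include ordinary night-to-night variation. They show that a mean cannot stand in for a count of individuals; they do not measure harm.

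**Step 3. What a count could show with 30 evaluable pairs.** If no participant met a chosen definition of worsening, the exact upper 95% limit would be 1 - 0.025^(1/30) = 11.6% (two-sided) or 1 - 0.05^(1/30) = 9.5% (one-sided). If the true rate were 5%, 10% or 20% (assumed), the chance of at least one case, 1 - (1 - p)^30, would be 78.5%, 95.8% or 99.9%. A tabulation is thus informative at this size, within wide limits.

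**Step 4. The stent offer beside the safety provisions.** The offer in 2.a, 8.e and 8.k states no condition on the device-night PSG. The close-out visit in 2.a discusses that PSG but attaches no decision to it. Section 9.d gives a general power to discontinue, with no PSG criterion. None of these refers to another, and it is not stated whether supply starts before or after the close-out visit.

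**The case against.** The case on the other side has five parts.

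- **Worsening is not ignored.** A higher AHI on the device night enters the primary comparison with its sign, and the unnamed PSG factors may include saturation. This stands: the gap is that nothing is tabulated per participant and nothing is labelled as safety.
- **A physician sees the results.** The close-out visit and the protocol director's power to discontinue allow judgement case by case. This also stands. A reader might infer that stents are supplied regardless of what the second PSG showed, or that the offer contradicts section 9.d. The documents do not support either reading. They are silent on the link, and an option to receive stents can coexist with a general safety override.
- **Section 9.e.i is mainly about data handling.** It says where forms, questionnaires and interviews are entered. A reader might infer that PSG results are barred from safety review; the text does not say so, and 9.d speaks of all safety data. What remains is that the one item headed as data for review does not mention the PSG.
- **Interviews suit the named risks.** Section 9.a lists nosebleed, soreness and swelling, which participants can report, and section 9.d also admits reports from healthcare providers. True, and the documents do not establish that worse breathing is the leading risk of the device. The point needs only that it is a possible harm that these routes detect poorly.
- **The counts would be noisy.** With one night per condition and no control arm, they cannot separate harm from variation; under the normal model a device with no effect gives 50% with a higher AHI. This limits interpretation and argues for description only. It does not argue for leaving the data out.

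**Conclusion.** The concern holds in a limited form. The SAP states a method for safety that leaves out the sleep recordings, so worsening of AHI, saturation or EKG on the device night is not counted as a safety outcome even though both PSGs capture it. This is a weakness in the stated method, and better use of existing data would remove it; the primary comparison is unaffected.

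Its size cannot be estimated from the documents. The illustrative 16% to 35% with a higher AHI (dz from 1.0 down to 0.37) rests on normal changes and 30 evaluable pairs, and includes night-to-night variation. It supports one conclusion only: a favourable mean can coexist with individual worsening. It should not be read as a harm rate.

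On the stent offer, the finding is that the passages are not linked. Neither a contradiction nor supply irrespective of the result has been shown.

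**What to change.** 1. **SAP, safety endpoint.** Add descriptive PSG-based outcomes, device night versus baseline: higher AHI; lower minimum SpO2 or more time at low saturation; any new EKG finding. Give a per-participant listing, and the number and percentage with exact (Clopper-Pearson) confidence intervals among participants with both PSGs evaluable. The investigator sets any threshold before the data are analysed; none is proposed here. Because section 2.a allows a repeat treatment PSG with another size, state which device night is used in the counts and list any repeat.
2. **SAP, interpretation.** State that, with one night per condition and no control arm, worsening is described and not attributed to the device.
3. **Protocol 9.e.i.** State that baseline and treatment PSG results are among the data the protocol director reviews.
4. **Protocol 2.a, 8.e, 8.k and 9.d.** Reconcile the stent offer with the close-out visit and the protocol director's safety decision, so that the reader can see whether and how they are connected. The rule itself is for the sponsor and the investigator.

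**Cost.** A few lines in the SAP, one table and one listing, one line in 9.e.i, and an edit to align the offer passages. No new measurement or visit is needed. The downside is that some flagged worsening will be night-to-night variation, and the report must say so.
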